Title: Comparison of fentanyl- bupivacaine and clonidine- bupivacaine for breakthrough pain in advanced labor in patients with continuous epidural analgesia

Columbia University Medical Center
Attached to Protocol: IRB-AAAL4101
Principal Investigator: [name]
Participation Duration: 1 day
Anticipated Number of Subjects: 250

PROTOCOL

Study Purpose and Rationale:

Epidural analgesia is a popular choice among patients for relief of severe pain associated with labor and delivery. Currently, at our institution we use a continuous infusion of low dose local anesthetic and narcotic (12 ml/hr of 0.0625% bupivacaine with 2 micrograms/ml fentanyl) after the initial spinal or epidural dose to maintain patient comfort until delivery. This dose of the infusion is chosen because it often provides adequate comfort without interfering with the mobility of the patient and her ability to effectively push during delivery. However, this low-dose epidural infusion strategy often results in recurrence of pain after an initial pain-free period. This recurring pain is known as breakthrough pain and is alleviated by administering small boluses of analgesics via the epidural catheter.

The pain occurring in labor is initially of visceral origin and is mediated by pain fibers originating from the low thoracic and upper lumbar segments of the spinal cord. As labor progresses to the late first phase (also known as transitional stage), pain sensations originating from the distension of the pelvic floor, vagina and perineum adds a somatic component to labor pain. This type of breakthrough pain, mediated by nerve fibers originating from the sacral nerves at dermatomes S2-S4, is often difficult to treat. Patients may experience inadequate analgesia even after boluses of analgesics are administered. Inadequate analgesia is deleterious due to subjective discomfort with its associated neurohumoral and physiological changes, and can be an initiator of the urge to bear down (push). Pushing before complete dilation of the cervix may lead to swelling, cervical injury and premature exhaustion of the mother. Adequate pain control will allow the cervix to fully dilate and motivate the mother to push effectively at the appropriate time. Although requests from patients to alleviate late stage breakthrough pain are common, there are no established data in the literature regarding the most effective strategy for pain management in this stage of labor.

This study is designed to compare the efficacy of two treatments for controlling late first stage breakthrough pain during labor: clonidine-bupivacaine versus fentanyl-bupivacaine. Both strategies are used at Columbia University Medical Center (CUMC) in this clinical situation, and there is no clear evidence whether one is superior.

Study Design and Procedures:

After obtaining consent, the patients will be randomized into two groups using a random allocation table. At the onset of late stage breakthrough pain with a Visual Analogue Scale (VAS) greater than or equal to 5/10, subjects will randomly receive either a mixture of 100 mcg

of clonidine and 12.5 mg of bupivacaine for a total volume of 10 ml ("CLON" group) and the other group will receive 100 mcg of fentanyl and 12.5 mg of bupivacaine for a total volume of 10 ml ("FENT" group). Group assignment will be performed by opening a previously prepared numbered opaque envelope containing the assignment "CLO" or "FENT".

The patient will be evaluated every 5 minutes for 15 minutes. If the patient reports a decrease in the VAS pain score by 4 points or more, the treatment will be declared a success. If the patient does not report a decrease in VAS score by 4 or more, the treatment will be declared a failure. If the treatment fails within 25 minutes from the end of injection of the initial study drug, the patient will receive the alternative of the initial treatment, which is 100 mcg of fentanyl or 100 mcg of clonidine (i.e., whichever drug was NOT given in the study mixture) with bupivacaine 12.5mg, diluted to a total of 10ml with sterile saline, via the epidural catheter (the observer will remain blinded to the identity of the medication). If this intervention fails to alleviate the pain, the caretakers will administer 5ml of 2% lidocaine via the epidural catheter. If the pain score still has not fallen by 4 or more points from baseline, 15 min after the dose of lidocaine the epidural catheter will be considered to be non-functioning.

All drug handling/distribution/administration will be conducted in accordance with the policies of the Research Pharmacy and Columbia University Medical Center.

Demographic and labor data (patient age, height, and weight, parity, hours in labor, cervical dilation and fetal station), details of labor analgesia preceding administration of the study drug (duration, type and amount of epidural or spinal analgesics, or other forms of analgesia), maternal and fetal heart rate and maternal blood pressure prior to and following administration of the study drug will be collected along with other clinical variables.

The study terminates upon delivery of the baby. Maternal and fetal hemodynamic data (maternal BP and pulse, fetal heart rate) and other clinical data will be obtained for 2 hours after the study dose, or until delivery, whichever is earlier. Neonatal Apgar scores as well as the mode of delivery will be collected.

Patients will be recruited by a study investigator after the establishment of labor epidural analgesia. The participants will be patients of the study team physicians. Informed consent with written documentation will be obtained from the research participant.

STATISITCAL PROCEDURES

The primary outcome is "success" or "failure" of the treatment as defined above. A clinically significant difference between the two treatments would be a 0.3 (30%) difference in probabilities for adequate analgesia. Assuming that the inferior treatment is successful in half of all patients, we aim to determine if the superior treatment is successful in 80%. For a power of 80% and an alpha of 0.05, this requires 45 subjects per group, so we plan on studying 100 overall.

To obtain 100 subjects who require a dose for breakthrough pain in the late first stage or second stage of labor, we may need to recruit and consent more than 250 subjects, since women will be

recruited after they are comfortable with their epidural analgesia, and it will not be known if they will eventually need a supplemental dose. Continuous data (VAS, total use of analgesics, maternal and fetal heart rate, maternal blood pressure) will be analyzed using ANOVA (with repeated measurements as appropriate) and categorical data (use of ephedrine, supplemental oxygen, fluid boluses and positional changes associated with administration of analgesics, instrumental delivery, cesarean section) will be analyzed using Chi-Squared analysis with Yates' continuity correction or Fisher's exact test as appropriate.

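### Does the unstated time of opening the allocation envelope leave the randomised and analysed women different?

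*Combined protocol and SAP*

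**What the plan says.** Study Design and Procedures in the combined protocol and SAP describes allocation in three sentences, in this order:

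- The first places randomisation relative to consent: "After obtaining consent, the patients will be randomized into two groups using a random allocation table".
- The second sets the trigger for dosing and again speaks of chance: "At the onset of late stage breakthrough pain with a Visual Analogue Scale (VAS) greater than or equal to 5/10, subjects will randomly receive". It goes on to list the two mixtures.
- The third gives the mechanism: "Group assignment will be performed by opening a previously prepared numbered opaque envelope containing the assignment". The arm label comes next.

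None of them gives the moment at which the envelope is opened. The same section says that women are recruited once the labor epidural is in place. It also says, where it describes the second treatment, that the observer stays blinded to the drug.

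The title block gives "Anticipated Number of Subjects: 250". Statistical Procedures says "we plan on studying 100 overall" and "we may need to recruit and consent more than 250 subjects", because at recruitment "it will not be known if they will eventually need a supplemental dose". The primary outcome is success or failure judged by the fall in VAS after the study dose. No analysis population is defined.

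**The concern.** The first sentence, read alone, instructs staff to randomise at consent. In many trials that would hardly matter, because consent and treatment are close together. Here the design separates them: a woman consents while comfortable and may never need the dose. A woman randomised at consent and never dosed has no primary outcome, and the plan does not say how she is handled.

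On that reading the analysed women are a subset selected after randomisation. The comparison is then protected only if whoever judged that a woman qualified did not know her arm. The opaque envelope gives that protection while it stays sealed, but the time of opening is the missing item. If knowledge of the arm affected who was dosed, the two dosed groups might no longer be comparable, and no analysis could fully repair that.

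**Working it through.** **Inputs.** Statistical Procedures gives success rates of 0.50 and 0.80, power 80%, alpha 0.05, 45 per group, 100 studied, and chi-squared with Yates' correction or Fisher's exact test for categorical data. The title block and Statistical Procedures give 250 consented. Assumptions: a two-sided test, 1:1 allocation and, for allocation at consent, exactly 250 women randomised 125:125 with need for a dose unrelated to arm.

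**The plan's own figure.** With mean proportion 0.65 and difference 0.30, the uncorrected size per group is

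n = [1.960 × √(2 × 0.65 × 0.35) + 0.842 × √(0.50 × 0.50 + 0.80 × 0.20)]² / 0.30² = (1.322 + 0.539)² / 0.09 ≈ 38.5, which rounds up to 39.

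The continuity correction gives

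n′ = (38.5/4) × [1 + √(1 + 4/(38.5 × 0.30))]² ≈ 44.9, which rounds up to 45.

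The stated 45 per group is reproduced. Exact power with Yates' correction is 0.807 at 45 per group and 0.853 at 50 per group.

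**Randomised women without an outcome.**

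- Allocation at dosing: 100 randomised, 100 dosed, 100 analysed; none missing, provided every woman whose envelope is opened is dosed and assessed.
- Allocation at consent: 250 − 100 = 150 undosed, and 150/250 = 60%.

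**Effect on power if only the dosed women are analysed after allocation at consent.** The number dosed in one arm is hypergeometric (250 women, 125 in the arm, 100 dosed), with mean 50 and SD √[100 × 0.5 × 0.5 × (250 − 100)/(250 − 1)] = √15.06 ≈ 3.9. The central 95% range is 42 to 58. Exact power at the edges of that range is:

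| Dosed, inferior : superior arm | Yates | Fisher |
|---|---|---|
| 50 : 50 | 0.853 | 0.853 |
| 42 : 58 | 0.849 | 0.867 |
| 58 : 42 | 0.834 | 0.859 |

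Every value exceeds the planned 80%.

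**Effect on bias.** An undosed woman has received neither study mixture. If her envelope is sealed when it is decided whether she qualifies, that decision cannot depend on her arm. The dosed women are then a selection unrelated to arm, and the comparison stands. Bias needs two further steps: the envelope is opened early, and the known arm then alters who is dosed. The documents describe neither.

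**Which reading the text favours.** The envelope sentence is the only one that says how assignment is carried out, and it follows directly on the sentence that sets the pain trigger. Statistical Procedures speaks of recruiting and consenting more than 250 women, not of randomising them, and of studying 100. The word after in the first sentence fixes an order, and allocation at dosing satisfies it.

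**The case for a change.** The strongest case for a change is that the favoured reading is inferred, not stated, and that two or three sentences would settle it. The explicit blinding statement concerns the observer and does not clearly cover whoever decides that a woman qualifies. The participants are patients of the study physicians, so that decision may lie with people close to the trial. Lost concealment cannot be restored in the analysis. All of this is correct as description. It shows that a detail is missing, but not that following the plan gives a wrong result. The trigger includes a numerical pain score reported by the woman, which limits discretion although it does not remove it. Counting opened envelopes against dosed women would also show whether any had been opened for a woman who was never dosed, though not what staff knew.

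It can also be argued that keeping all 250 women would be costly. The 30-point difference would shrink to 0.4 × 30 = 12 points, and exact Yates power would be 0.53 with undosed women coded as failures or 0.74 with them coded as successes. The arithmetic is right, but the documents propose neither coding, and the outcome is defined only after a study dose. These figures do not measure the effect of the missing detail.

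Finally, the qualifying stage is worded in two ways. Study Purpose and Rationale refers to "controlling late first stage breakthrough pain during labor", while Statistical Procedures also admits the second stage. The mismatch is real, but it is a separate matter of wording that does not depend on envelope timing, and no effect on the comparison of arms has been shown.

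**Conclusion.** The concern does not call for a change. The time of opening is unstated, but the sequence of the text and the planning numbers point to allocation at dosing, where the randomised and analysed women coincide. On the less natural reading, 150 of 250 women would have no outcome. Analysing the dosed women by assigned arm would still give exact Yates power of 0.834 or more across the central 95% range of splits, and no bias arises while envelopes stay sealed until a woman qualifies. Analysts would sensibly analyse the dosed women in their assigned arms and report those who consented but were never dosed in the participant flow.

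The power results assume 250 women split 125:125, 100 of them dosed, the plan's 0.50 and 0.80, and a two-sided test. The judgement on bias assumes that the envelopes conceal the arm until the dosing decision. The documents do not say this outright, but nothing in them contradicts it. The sample size of 45 per group and 100 overall is unaffected.

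### Success is a fixed 4-point VAS fall from a baseline of 5 or more, but the named tests ignore baseline VAS; prespecified adjustment is an optional gain of unknown size

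*Combined protocol and SAP*

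**What the plan says.** Under Study Design and Procedures, dosing is triggered by "late stage breakthrough pain with a Visual Analogue Scale (VAS) greater than or equal to 5/10", and the responder rule is absolute: "If the patient reports a decrease in the VAS pain score by 4 points or more, the treatment will be declared a success". The reference point is spelled out only for the later lidocaine step ("If the pain score still has not fallen by 4 or more points from baseline"), but a fall in VAS can only be measured from the pre-dose reading.

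The statistical section makes this the primary endpoint: "The primary outcome is 'success' or 'failure' of the treatment as defined above". It lists "categorical data (use of ephedrine, supplemental oxygen, fluid boluses and positional changes associated with administration of analgesics, instrumental delivery, cesarean section") and says these "will be analyzed using Chi-Squared analysis with" Yates' correction, or Fisher's exact test. Success/failure is not in that list, so its test has to be inferred. VAS as a continuous measure "will be analyzed using ANOVA (with repeated measurements as appropriate"). No covariate, stratification factor or adjusted model is named anywhere. The sample size statement is: "For a power of 80% and an alpha of 0.05, this requires 45 subjects per group, so we plan on studying 100 overall".

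**The concern.** A fixed 4-point fall is a harder target for a woman who starts at VAS 5 than for one who starts at VAS 10. If relief scales at all with the starting score, baseline VAS predicts success in both arms, and a test that ignores it leaves some outcome variation unexplained. The repeated-measures ANOVA may use the pre-dose reading for continuous VAS, but it does not reach the binary primary outcome.

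What is at stake is precision, not validity. The number analysed is fixed at 100, and the trial must already record the pre-dose VAS to apply its dosing criterion and success rule. Using that value might narrow the interval around the treatment difference at no data cost. Adjustment chosen after the data are seen would not be credible, so the decision belongs in the plan.

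**Working it through.** **Inputs.** From Study Design and Procedures: baseline VAS at least 5, fall of at least 4. From the statistical section: success 0.50 v 0.80, power 0.80, alpha 0.05, 45 per group, 100 overall. Sidedness is not stated, but two-sided reproduces the sample size. 1:1 allocation is inferred from the equal group sizes.

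**1. The plan's sample size.** With mean rate 0.65, n = [1.96√(2 × 0.65 × 0.35) + 0.842√(0.50 × 0.50 + 0.80 × 0.20)]² / 0.30² = (1.322 + 0.539)² / 0.09 = 38.5 per group. The continuity-corrected value is (n/4)[1 + √(1 + 4/(0.30n))]² = 44.9, rounded up to 45. The plan's figure is reproduced and is consistent with a Yates test.

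**2. Exact power, 50% v 80%** (full enumeration of both binomials).

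| Per arm | Yates | Fisher | Uncorrected Pearson |
|---|---|---|---|
| 45 | 0.807 | 0.815 | 0.868 |
| 50 | 0.853 | 0.853 | 0.895 |

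**3. Relief needed.** The required fraction is 4/baseline: 4/5 = 80% at VAS 5, 4/8 = 50% at VAS 8, 4/10 = 40% at VAS 10.

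**4. Gain from adjustment.** The documents give neither a baseline VAS distribution nor its relation to success, so both are assumed. Baseline VAS 5 to 10 has weights .10/.15/.25/.25/.15/.10 (spread) or .03/.12/.35/.35/.12/.03 (narrow). Each model has 50 per arm, 50% v 80% success and 20,000 simulated trials (Monte Carlo SE about 0.002). Entries are Pearson power / adjusted likelihood-ratio power / ratio of adjusted to unadjusted variance of the risk difference.

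| Assumed relation | Success in 50% arm, VAS 5 v 10 (spread) | Spread | Narrow |
|---|---|---|---|
| Relief proportional to baseline, SD .25 | 16% v 73% | .895 / .928 / .906 | .895 / .913 / .955 |
| Same, SD .35 | 24% v 67% | .897 / .915 / .952 | .897 / .909 / .982 |
| Fraction relieved drops .04 per point, SD .25 | 28% v 59% | .897 / .907 / .981 | .895 / .900 / 1.000 |
| Same, SD .35 | 34% v 56% | .897 / .903 / .997 | .893 / .897 / 1.004 |
| Fraction relieved drops .08 per point, SD .25 | 43% v 43% | .894 / .895 / 1.009 | .896 / .899 / 1.013 |
| Same, SD .35 | 45% v 45% | .896 / .898 / 1.008 | .897 / .898 / 1.012 |
| Post-dose level unrelated to baseline, SD 2 | 11% v 89% | .897 / .956 / .804 | .897 / .934 / .894 |
| Fall unrelated to baseline, SD 2.5 | 50% v 50% | .898 / .900 / 1.009 | .891 / .893 / 1.010 |

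The gain over Pearson is 0.0 to 5.9 points (taken before rounding, so subtracting table entries can differ by 0.1). A gain of 1 point or more appeared only where success in the 50% arm rose by about 30 points or more from VAS 5 to VAS 10.

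**5. Separate check.** Let baseline explain a share R² of the outcome variance. At 50 per arm, power = Φ[(0.30 − 1.96·SE₀)/SE₁], with SE₀ = √(0.65 × 0.35 × 2/50 × (1 − R²)) and SE₁ = √(0.41/50 × (1 − R²)). For R² = 0, .02, .05, .10 and .20, power is 89.4%, 90.0%, 90.9%, 92.3% and 94.9%, a gain of 0 to 5.5 points. A simulation with uniform baseline and odds ratios per VAS point of 1.00, 1.22, 1.35 and 1.65 gives adjusted power of 89.7%, 90.0%, 91.2% and 93.1%, against about 89% unadjusted throughout.

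**6. Type I error at 50 per arm.** For common rates .50/.60/.65/.70/.80, exact values are Yates .035/.032/.030/.031/.028 and Pearson .057/.052/.049/.050/.052. Over 48 null scenarios the adjusted likelihood-ratio test gives .048–.057, and a 95% interval for the risk difference excludes 0 in .052–.062. Test and interval disagree in 0.3–0.6% of null trials and 0.2–0.8% at 50% v 80%, where interval coverage is .940–.945.

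**The case against.** The strongest reply is that nothing is wrong. Randomisation makes the unadjusted comparison valid, 45 per group fits the named Yates test, and power exceeds the target at 50 per arm. In 7 of the 16 models adjustment makes the variance slightly worse (ratios 1.004 to 1.013), and in two more it is essentially unchanged (0.997 and 1.000). The same nine gain less than 1 power point. The 5.9-point maximum needs a post-dose level unrelated to baseline, with success climbing from 11% to 89% across the VAS range. Part of the small gains is not precision: where the variance ratio exceeds 1, adjusted power is still slightly above Pearson, because the likelihood-ratio test is a little liberal. The change also gives up a conservative test for one nearer the nominal level. Finally, the success rule has a timing question of its own, with evaluation over 15 minutes but failure referred to within 25.

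All of this stands, and it limits the point to an optional suggestion. It does not remove it: a plausibly prognostic value that the trial must record is unused in the primary comparison, and the loss if it proves uninformative is about 1% of variance. The 15- and 25-minute statements are a separate matter to reconcile. The absence of success/failure from the categorical list is a gap in wording, and the conclusion does not rest on it.

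**Conclusion.** The point holds as an optional improvement of low priority, not as an error. The unadjusted test is valid and adequately powered on the plan's own assumptions, and no change in sample size follows.

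The benefit of adjusting for baseline VAS is unknown. Under the assumed models it runs from nothing to 5.9 power points, with the variance of the risk difference between 20% lower and 1% higher. It is worth a point or more only if success rises steeply with baseline, by about 30 percentage points or more from VAS 5 to VAS 10. The further 0.895 − 0.853 = 0.042, about 4 points, over the Yates test comes from dropping the continuity correction and should not be credited to adjustment.

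**What to change.** Before any data are seen, name success/failure in the statistical section and specify its primary analysis: logistic regression of protocol-defined success on arm, with VAS at study-drug administration as a continuous covariate. State that the likelihood-ratio test for arm governs the conclusion. Report the standardised risk difference (predicted success under each arm, averaged over all analysed patients' baseline values) with a 95% interval, which stays on the scale of the plan's 0.3 target. Keep Yates or Fisher as the sensitivity analysis, and say that it stands in if the model does not converge.

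The likelihood-ratio test is the better choice to govern because its type I error (.048–.057) is closer to nominal than that of the interval (.052–.062).

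The cost is plan wording only, with no new data and 100 patients as before. The drawbacks are about 1% of variance lost if baseline is uninformative, type I error of about 0.05–0.06 in place of roughly 0.03 under Yates, and a test and interval that disagree on significance in under 1% of trials. If the team prefers to stay unadjusted, stating which test applies to success/failure is enough.

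### Blood pressure and heart-rate series that stop at delivery are left to repeated-measures ANOVA, with no stated role for pre-dose values and no stated window or rule for readings after crossover rescue

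*Combined protocol and SAP*

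**What the plan says.** Under Study Design and Procedures, the stated aim is to "compare the efficacy of two treatments for controlling late first stage breakthrough pain during labor: clonidine-bupivacaine versus fentanyl-bupivacaine". On measurement, the protocol says that "maternal and fetal heart rate and maternal blood pressure prior to and following administration of the study drug will be collected". Follow-up of maternal blood pressure continues with "pulse, fetal heart rate) and other clinical data will be obtained for 2 hours after the study dose, or until delivery, whichever is earlier". The same section adds: "The study terminates upon delivery of the baby".

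Rescue falls inside that period. The protocol says "The patient will be evaluated every 5 minutes for 15 minutes". It then words the condition for rescue as follows: "If the treatment fails within 25 minutes from the end of injection of the initial study drug". In that event, the protocol provides that "the patient will receive the alternative of the initial treatment, which is 100 mcg of fentanyl or 100 mcg of clonidine", given with a further 12.5 mg of bupivacaine. If that does not work, "the caretakers will administer 5ml of 2% lidocaine via the epidural catheter".

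The Statistical Procedures section assigns VAS, total analgesic use, heart rates and blood pressure to ANOVA, in repeated-measures form where suitable. Ephedrine, oxygen, fluids and repositioning linked to analgesic dosing go to chi-squared or Fisher tests. The section expects some women to be dosed in the second stage of labor. It gives no analysis window for the haemodynamic data, no rule for readings after rescue, no handling of shortened series and no use for the pre-dose values.

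**The concern.** Two gaps affect the haemodynamic results.

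The first is the method. Classical repeated-measures ANOVA expects every woman to have a reading at every time. A woman who delivers early has a short series, and the usual procedure either drops her or handles her readings badly. Women dosed late in labor are the most likely to be lost. The pre-dose values could sharpen the comparison, but the plan does not say whether they are a covariate, a reference for change or one level of the time factor.

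The second is what the comparison would mean. A woman whose first mixture fails receives the other arm's drug, so later readings in both arms include women who have had both drugs. If all collected readings are analysed by assigned arm, the result describes assignment to a strategy. A reader asking whether one initial mixture changes blood pressure or fetal heart rate more than the other would find no planned comparison aimed at that question.

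**Working it through.** **The plan's own figure.** Inputs from Statistical Procedures: success 0.50 and 0.80, alpha 0.05, power 80%.
- Uncorrected, two-sided: n = [1.96·√(2·0.65·0.35) + 0.8416·√(0.5·0.5 + 0.8·0.2)]² / 0.3² = 38.5, so 39 per group.
- With continuity correction: (38.5/4)·[1 + √(1 + 4/(38.5·0.3))]² = 44.9, so 45 per group.

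The stated 45 reproduces exactly. It concerns the primary outcome; the documents give no figure for the haemodynamic comparison.

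**Women who receive both drugs.** With 100 women split 50 and 50, and every failure receiving the alternative: 50·0.5 + 50·0.2 = 25 + 10 = 35. The variance is 50·0.25 + 50·0.16 = 20.5, so the 95% sampling range is 35 ± 1.96·4.53, or about 26 to 44.

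**Share of follow-up after rescue.** Assumption, taken from the two times in the protocol: rescue at 15 to 25 minutes. For a rescued woman with a full 2 hours:
- (120 − 25)/120 = 0.79 to (120 − 15)/120 = 0.88.
- Arm failing 50%: 0.5 × (0.79 to 0.88) = 40–44% of arm follow-up.
- Arm failing 20%: 0.2 × (0.79 to 0.88) = 16–18%.

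These are upper-end figures, because they assume that nobody delivers before 2 hours. As a sensitivity check, suppose an exponential time to delivery with a median of 1 hour, independent of failure. The share of observed time after rescue at t minutes is then [2^(−t/60) − 0.25]/0.75, which is 0.67 at 25 minutes and 0.79 at 15 minutes. The arm failing 50% then has 33–39% of its observed time after rescue.

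**Incomplete series (illustration only).** With exponential time to delivery and median m hours, the share with a complete 2-hour series is 2^(−2/m): 25% at 1 hour, 50% at 2 hours, 71% at 4 hours. The documents give no delivery-time distribution.

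**Meaning of a full-window mean difference (illustration only).** Assume additive, immediate and lasting effects and no early delivery. Let c be the clonidine-minus-fentanyl difference between the initial mixtures, b the further effect of any second dose, s the post-rescue share, and fC and fF the failure rates.
- CLON mean = c + fC·s·b; FENT mean = fF·s·(c + b).
- Difference = c(1 − fF·s) + (fC − fF)·s·b.
- Multiplier of c: 0.56–0.60 if FENT fails 50%, 0.69–0.72 if 35%, 0.83–0.84 if 20%.
- Coefficient of b: +0.24 to +0.26 for (fC, fF) = (0.5, 0.2), the same size but negative if swapped, and 0 if equal.

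The direction is therefore not known in advance.

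**Value of the pre-dose covariate (illustration only).** At an assumed correlation ρ of 0.5 to 0.7, the variance reduction is ρ² = 25–49% against post-dose values alone. Against change from baseline it is 1 − (1 − ρ²)/[2(1 − ρ)] = (1 − ρ)/2 = 25–15%.

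**The case against.** A reader might infer that the plan commits itself to a 2-hour comparison contaminated by rescue, and that this is an analysis error. The documents do not support that. The 2 hours is a period of data collection, and the statistical section names no analysis window at all. The aim is framed as efficacy against pain, with no haemodynamic objective tied to the initial mixtures. An as-assigned comparison over all readings is a legitimate randomised comparison of strategies. The early-window analysis is therefore a supplement, not a correction.

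The plan's qualifier on repeated measures leaves room for a suitable model, and a pre-dose reading could enter as one level of the time factor. The interventions are described as linked to analgesic dosing, which may already tie them to particular doses. The early window is short, and with no haemodynamic schedule it may hold few readings or none. The larger numbers rest on no early delivery and on instant, lasting effects.

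All of this is fair and limits the point. What remains is that leaving room for a model does not specify one. Shortened series are certain to be an issue when collection ends at delivery, and nothing tells the analyst how to treat readings after rescue. Nor may a reader extend the point to the primary outcome, which is the success or failure of the first treatment and is not defined by these readings.

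**Conclusion.** The point holds as a gap in the specification of secondary analyses that is cheap to close. The method named suits unequal series poorly, the pre-dose values lack a stated role, and the window and handling of post-rescue readings are unstated.

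The firmest figure is about 35 of 100 women receiving both drugs. It rests only on the plan's success rates, an even split and every failure being given the alternative. The 40–44% post-rescue share in the arm that fails more is an upper-end figure and falls to 33–39% under a 1-hour median to delivery. The multipliers, delivery-time shares and variance gains show what could happen under assumptions absent from the documents; they are not estimates for this trial.

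**What to change.** 1. For blood pressure and heart rates, specify a linear mixed model with arm, time, arm-by-time and the pre-dose value as covariate, using all readings up to delivery. Interpret the results as values while undelivered, and report the number undelivered at each time.
2. Keep the full-window as-assigned analysis and label it a comparison of strategies including crossover rescue. Record the times of the second drug, of lidocaine and of each intervention.
3. As a supplement, compare the arms as assigned, in all dosed women, over one fixed early window ending at the earliest time rescue may be given. Using the same cut-off for everyone avoids conditioning on treatment failure. The sponsor must first reconcile the 15- and 25-minute statements, and confirm that at least one post-dose haemodynamic reading falls in the window. If readings were taken at the 5-minute evaluations, 15/5 = 3 would fall by 15 minutes, but the documents do not say so.

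The cost is SAP wording and a few time fields on the case report form. The early window is short, will contain few events and may miss later effects, so it should be reported beside the full-window analysis. Later time points in the model rest on fewer women, and they are not a fully randomised comparison if time to delivery differs by arm.
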